### **Anamnesis, physical examination, and competition**

At the beginning of the study, all participants will undergo an anamnesis with a cardiovascular and otorhinolaryngological analysis to exclude the presence of cardiovascular diseases and upper airway symptoms resulting from rhinosinusitis, rhinopathies, or any other pre-existing alteration in these systems. In addition, the WURSS (Wisconsin Upper Respiratory Symptom Survey) questionnaire will be used to verify the occurrence of upper airway symptoms not only during this period but also throughout the study period (Annex 1), and the presence of premenstrual syndrome will be self-reported by the female volunteers during the anamnesis.

It is noteworthy to cite that the volunteers will be oriented to maintain their usual daily routine, including sleep, diet, and training/physical activity during the study performance. In this respect, to characterize not only the quality of life (Annex 2) but also the level of physical activity (Annex 3), questionnaires will be applied with open questions about the participants' lifestyle and habits, history and current habits of physical activity, as well as participation in competitions. Beyond these questionnaires, it will be also assessed the occurrence of discomfort or gastrointestinal problems related to the daily intake of fermented milk containing LcS or not by using a questionnaire with open questions about gastrointestinal problems will be used (Annex 4). The volunteers who reported any gastrointestinal discomfort during the ingestion of the fermented milk containing or not LcS will be oriented to immediately interrupt this ingestion and seek medical assistance. In case of the volunteer needs to interrupt the ingestion of fermented milk for five consecutive days, following medical recommendation, this volunteer and its data will be excluded from the study.

It is utmost of importance to point out that all athletes will have medical follow-ups by [name] [name], a specialist in Sports Medicine, throughout the study. Besides, through social media, all volunteers will be able to directly contact not only [name] but also other researchers involved in the study's development in order to communicate any adverse events and other unintended effects of trial interventions.

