### **LcS ingestion**

After stratification, the volunteers will be separated into two groups: (1) LcS Group (LcSG), which will ingest 1 bottle of fermented milk (80 grams) with  $40 \times 10^9$  of LcS per day; and (2) placebo/unfermented milk Group (PLG), which will consume 1 bottle of unfermented milk (80 grams), due to the absence of LcS. Both groups will begin the ingestion 30 days before the competition, maintaining it until 14 days after the competition. As previously mentioned, all volunteers will be oriented to stop drinking immediately and seek medical attention if any symptoms of gastrointestinal disturbance are perceived. To ensure the development of a double-blind study, all bottles used in the study will be kindly provided by YAKULT S/A Industria e Comércio, Brazil. The bottles will be named A and B by the company and will have the same taste, appearance, and smell. Information on the presence or absence of LcS in the bottles will be accessed only after all analyzes have been performed. In addition, to monitor the adherence of volunteers to the study's protocol, we intend not only to request the return flask fortnightly (empty or not) but also to maintain routine contact via social media with the volunteers. This contact also will allow us to provide responses and orientations to any questions by them, as well as, weekly, to perform auditing concerning the study's conduction.

It is important to clarify that the Yakult S/A Industria e Comércio, Brazil, will provide the fermented milk containing LcS and also the placebo/unfermented milk. In addition, Yakult Honsha Co., Ltd. Japan, will fund the development of the study, which includes all the materials needed to perform the collection, procedures, storage, and laboratory evaluations of

the biological samples obtained on all occasions described in the study. Besides, it is noteworthy to mention that the design, management, data check and analysis, and preparation of the reports/articles of the study are entirely under the responsibility of the researchers.

Regarding the ingestion period, it is based on the study by [name] et al. (2019), which showed a remarkable capacity of fermented milk containing LcS in modulating several immune/inflammatory parameters, both systemic and in the upper airways, in runners after a marathon.

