### **Statistical analysis**

All data obtained during the development of this study will be added to a unique file, preferentially in an Excel file, which will be available to all researchers not only to consult and check the data quality/accuracy but also to add any results through GOOGLE-DRIVE. It is noteworthy to clarify that, to perform all the statistical analysis proposed here, we will follow the "intention-to-treat" (ITT) analysis, not only because it is recommended as an analysis strategy for randomized studies but also to be possible to maintain the sample size, as well as to use the data obtained from the participants regardless of whether they complete the study since ITT considers all randomized participants in the analysis, whether they drop out or not. In addition, the multiple imputation (MI) method will be applied to handle missing data since

MI fills in missing values by generating plausible numbers derived from distributions of and relationships among observed variables in the data set. Beyond these analyses, in order to check and increase the reliability of the results obtained in the ITT analysis, we also intend to conduct the statistical analysis regarding the per-protocol (PP) analysis, which will be used exclusively the complete data obtained from the volunteers.

After all data will be added to the Excel file and the data quality/accuracy is checked by the researchers, these data will be initially compared with the Gaussian curve, and normality determined for each variable.

If the variable presents a parametric behavior, the mean and standard deviation will be used, and they will be compared by using the ANOVA test for repeated measures with post hoc tests for intragroup (longitudinal) and intergroup (cross-sectional) analysis.

On the other hand, if the data present a non-parametric behavior, they will be represented by median and interquartile ranges, and they will be compared by using Friedman's test with Müller-Dun post hoc test for intragroup (longitudinal) and the Kruskal-Wallis test with Müller Dunn's post hoc test for intergroup (cross-sectional).

Using Pearson (for parametric values) or Spearman tests (for non-parametric values), the correlation between the variables studied will be evaluated.

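### Data of athletes who stop intake for five consecutive days on medical recommendation are deleted after randomisation, which contradicts the planned intention-to-treat analysis

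*Combined protocol and SAP*

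**What the plan says.** Three parts of the protocol bear on this point.

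- **Deletion rule** (Anamnesis, physical examination, and competition). It applies when a volunteer "needs to interrupt the ingestion of fermented milk for five consecutive days, following medical recommendation". The consequence is that "this volunteer and its data will be excluded from the study". The sentence before it tells athletes with gastrointestinal discomfort during intake to stop drinking the product and seek medical help.
- **Timing** (LcS ingestion). "After stratification, the volunteers will be separated into two groups", and then "Both groups will begin the ingestion 30 days before the competition, maintaining it until 14 days after the competition". The Cardiopulmonary Test section describes randomisation within strata, and the schedule of activities puts randomisation at allocation, ahead of intake.
- **Analysis rule** (Statistical analysis). ITT is adopted for all analyses, on the grounds that "ITT considers all randomized participants in the analysis, whether they drop out or not" and in order "to use the data obtained from the participants regardless of whether they complete the study". In addition, "the multiple imputation (MI) method will be applied to handle missing data". A per-protocol analysis is added as a check, for "which will be used exclusively the complete data obtained from the volunteers".

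A further rule is relevant only conditionally. Exclusion criterion 6 under Population and design of the study removes any participant with missing data. It sits in a list introduced by the initial clinical examinations.

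**The concern.** An athlete whose data have been removed from the study cannot also be in an analysis of everyone randomised. For such an athlete, one section deletes the record and the other keeps it and imputes what is missing. Two analysts following this plan in good faith could analyse the primary endpoint, salivary IgA, in different populations.

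The exclusion is also not a neutral one. It depends on something that happens after allocation and, judging by the preceding sentence, may reflect tolerability of the assigned product. The arms receive different products, fermented milk with LcS and unfermented milk, so equal interruption rates cannot be taken for granted. Blinding does not protect against this, because the selection would act through the effects of the product itself.

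**Working it through.** **1. Is the event after randomisation?** Groups are formed first, and intake then runs from 30 days before to 14 days after the competition. An interruption of intake can therefore only follow allocation.

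**2. Can both rules hold?** The deletion rule covers the person and the data, and its scope is the study. The ITT rule covers all randomised participants, whether or not they drop out. They could be reconciled if the deletion applied only to the per-protocol set. However, the Statistical analysis section defines that set by complete data alone. It names no adherence or five-day criterion, and no other section supplies the link.

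**3. What could deletion do to the comparison?** Suppose k of n athletes in one arm are deleted and none in the other. Let the deleted athletes differ from the rest of their arm by a constant c in IgA level at every visit, plus D in change from baseline.

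- Deletion shifts that arm's baseline mean by (k/n) × c.
- It shifts each post-baseline mean by (k/n) × (c + D).
- The difference between groups in change therefore shifts by (k/n) × D. The level term c cancels from the group-by-time interaction, which is the test the sample size is built on. It would still affect the cross-sectional intergroup comparisons.

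The documents give neither k nor D, so the following values are assumptions (n = 35 to 40 is the planned arm size):

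- k = 1, n = 40, D = 0.25 SD: 1/40 × 0.25 = 0.006 SD
- k = 2, n = 35, D = 0.5 SD: 2/35 × 0.5 = 0.029 SD
- k = 4, n = 35, D = 1.0 SD: 4/35 × 1.0 = 0.114 SD

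For scale, take a group difference d that is zero at baseline and constant at the other four visits. The interaction SD is then 0.5 × d × √(0.8 × 0.2) = 0.2d. The planned f = 0.15 therefore corresponds to d = 0.15/0.2 = 0.75 SD. The three shifts are 0.8%, 3.8% and 15.2% of that.

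**4. Is the sample size affected?** The inputs from Population and design of the study are f = 0.15, alpha = 0.05, five measurements, two groups, correlation 0.5 and nonsphericity correction 1. The noncentral F calculation uses λ = f² × N × 5/(1 − 0.5), df1 = 4 and df2 = 4(N − 2).

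- At N = 62: λ = 0.0225 × 62 × 10 = 13.95, df2 = 240, power 0.857. At N = 60, power is 0.844. With equal groups, the stated 62 reproduces.
- At N = 70 and 80, power is 0.902 and 0.940. These are upper limits for ITT with imputation, because imputation does not restore unobserved values.
- The number analysed falls below 62 only if more than 70 − 62 = 8 athletes (8/70 = 11.4%) or more than 80 − 62 = 18 athletes (18/80 = 22.5%) are lost.

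**The case against.** The strongest reply is that the deletion rule stands in a conduct section, where exclusion from the study may mean no more than withdrawal. The Statistical analysis section is the only place that sets analysis populations. It puts ITT over all analyses and provides a per-protocol analysis in which such athletes could be dropped. This has some force: the intended main analysis can be recovered, and a reader who concluded that the plan lacks an ITT analysis would be wrong. It does not remove the conflict, because the rule names the data as well as the volunteer.

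The trigger is also narrow. It needs five consecutive days and a medical recommendation, athletes reporting lactose intolerance are excluded at entry, and both arms drink a milk product. The rule does not itself restrict the reason for interruption, so the link to gastrointestinal symptoms is an inference from the preceding sentence. These points stand, and they are why no bias can be asserted as likely or large.

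Two stronger readings are tempting, but the documents do not support them:

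- **Loss of power.** A reader might infer that deletions leave the trial too small. The planned 70 to 80 athletes leave room for 8 to 18 losses before the number falls below 62, and no expected loss is stated.
- **Collapse of ITT into per-protocol.** If criterion 6 were applied after randomisation, nothing would be left to impute and the two analyses would use the same athletes. But the criterion follows the initial clinical examinations, and screening is its natural reading. It needs clarification; it is not a second proven contradiction. The ethics opinion repeats the rule but describes a differing version with 60 to 70 participants, so it settles nothing.

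**Conclusion.** The contradiction is real and stands in the current text: a post-randomisation deletion of athletes and their data conflicts with ITT of all randomised participants, and nothing limits the deletion to the per-protocol set. This conclusion needs no assumed rate.

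Bias in the randomised comparison is possible but not shown. For the interaction test it requires both unequal interruption between arms and a different change in salivary IgA among the deleted athletes. Its size is unknown. The range of 0.006 to 0.114 SD rests on assumed values of k and D, and its upper end needs four deletions in one arm of 35, none in the other and a full 1 SD difference in change. The comparison with 0.75 SD further assumes an effect held constant over the four post-baseline visits.

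The matter should be settled before outcome data are seen, since a later choice of population would be open to challenge.

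**What to change.** Make three changes of wording:

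1. **Anamnesis, physical examination, and competition:** replace the deletion of data with a statement that data already collected stay in the ITT analysis in the randomised group. Later visits are also used where the athlete continues to attend, and missing values are handled by the multiple imputation already planned.
2. **Statistical analysis:** state that the five-day interruption rule and the completeness rule define only the per-protocol set.
3. **Population and design of the study:** clarify that criterion 6 refers to screening data, before randomisation.

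The clinical rule on when intake is interrupted is not touched. The cost is the redrafting, an ethics amendment (the Recommendations in the ethics opinion require protocol changes to be submitted as one) and slightly more imputation work. The investigators must also decide whether athletes who stop intake are still invited to the sample visits. That is a follow-up procedure and not only wording. No extra participants are needed.

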## **Evaluation of the External Training Load**

The external training load will be determined by the sum of time dedicated to each training modality (swimming, cycling, and running), besides the time spent in each of the intensity zones (light, moderate and intense) during the training weeks.

## **Evaluation of the Internal Load of Training**

The internal training load will be established by the relationship between the time dedicated to training and the subjective perception of the effort of the session (PSE-session), which is determined through the use of the subjective effort scale modified by Foster et al. (1998), as proposed by Impellizzeri et al. (2004).

Soon after the exercise session, the Borg CR-10 (Borg Category-Ratio) scale adapted by Foster (1998) will be presented to athletes (Annex 5).

Therefore, the internal training load values obtained from this relationship will be expressed in arbitrary units (AU).

## **Cardiopulmonary Test**

The physical capacity of each volunteer will be characterized through a cardiopulmonary test that will be performed on a treadmill attached to the gas analyzer, with electrocardiography and gas analysis software. This test will be performed at the Research and Training Olympic Center, an institution belonging to the Municipal Secretariat of Sports, Leisure, and Recreation of the City of São Paulo.

In order to carry out the cardiopulmonary test, the patient's preparation rules will be followed, which include hair removal from the place where the electrodes will be placed, cleaning the skin with alcohol, and scarification with water sandpaper number 400. The placement of the electrodes will follow the described by Salient (2019) for the formation of the 12 leads in the Einthoven triangle.

The cardiopulmonary test will be performed with a ramp protocol, with a fixed incline of 1% and load increment (1km/h) every minute until the maximum speed of the treadmill, at which time the increment of 2% incline begins every minute. The protocol should be started

with 10.9 or 8 km/h according to the time for a 10 km race, with the time below 35', between 35' and 46', and above 46', respectively. Tests should be maximum, being interrupted by limiting symptoms / intense physical fatigue.

The data obtained in this test in conjunction with body composition will be used to stratify the volunteers into four different strata. In addition, the randomization of volunteers in each strata will follow the process: firstly, the researcher [name], will be responsible for creating a computer-generated random list of numbers for the treatment groups of either LcS or placebo, and after each volunteer will be anonymously and sequentially allocated in these groups according to their recruitment ordering number in the program.

### **LcS ingestion**

After stratification, the volunteers will be separated into two groups: (1) LcS Group (LcSG), which will ingest 1 bottle of fermented milk (80 grams) with  $40 \times 10^9$  of LcS per day; and (2) placebo/unfermented milk Group (PLG), which will consume 1 bottle of unfermented milk (80 grams), due to the absence of LcS. Both groups will begin the ingestion 30 days before the competition, maintaining it until 14 days after the competition. As previously mentioned, all volunteers will be oriented to stop drinking immediately and seek medical attention if any symptoms of gastrointestinal disturbance are perceived. To ensure the development of a double-blind study, all bottles used in the study will be kindly provided by YAKULT S/A Industria e Comércio, Brazil. The bottles will be named A and B by the company and will have the same taste, appearance, and smell. Information on the presence or absence of LcS in the bottles will be accessed only after all analyzes have been performed. In addition, to monitor the adherence of volunteers to the study's protocol, we intend not only to request the return flask fortnightly (empty or not) but also to maintain routine contact via social media with the volunteers. This contact also will allow us to provide responses and orientations to any questions by them, as well as, weekly, to perform auditing concerning the study's conduction.

It is important to clarify that the Yakult S/A Industria e Comércio, Brazil, will provide the fermented milk containing LcS and also the placebo/unfermented milk. In addition, Yakult Honsha Co., Ltd. Japan, will fund the development of the study, which includes all the materials needed to perform the collection, procedures, storage, and laboratory evaluations of

the biological samples obtained on all occasions described in the study. Besides, it is noteworthy to mention that the design, management, data check and analysis, and preparation of the reports/articles of the study are entirely under the responsibility of the researchers.

Regarding the ingestion period, it is based on the study by [name] et al. (2019), which showed a remarkable capacity of fermented milk containing LcS in modulating several immune/inflammatory parameters, both systemic and in the upper airways, in runners after a marathon.

In order to obtain the best quality in our results, we will follow the experimental design described below (Figure 1), highlighting that some procedures will be performed on the same day of sample collection.

[figure not shown]

Figure 1 - Study design.

### Triathlon competition

It is important to clarify that the volunteers will perform the same triathlon competition, which will be part of the annual calendar for this type of sport. In this respect, it is worth mentioning that we intend to carry out the study by inviting the athletes that will perform the IronMan 70.3 São Paulo in 2025, which, in a general way, occurs in September, and is

composed of 1,900 meters of swimming, followed by 90 km of cycling, and 21 km of running (<https://www.ironman.com/im703-sao-paulo>).

Besides, to motivate and ensure that all volunteers will perform the competition with maximal effort, the official time of each volunteer to end the competition, obtained through the data available by the organizing committee of the competition, will be used to define their ranking in the present study and, consequently, the best triathletes in this competition.

### **Sample collection**

Blood, saliva, and nasal swab will be collected on five different occasions: (1) before the beginning of the ingestion of fermented milk containing LcS or placebo; (2) 24 hours before the triathlon competition; (3) immediately (IM); (4) 72 hours (post-72h); and (5) 14 days after the competition, as shown in Figure 1. In addition, on the same occasions, the occurrence of upper airway symptoms and mood states will also be assessed by using questionnaires.

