## ABSTRACT

Triathlon, as a sport that combines high-intensity and long duration, imposes the body to an expressive physiological adaptation. However, when the challenge exceeds the physiological adaptation capacity, it is possible to observe the occurrence of several disorders in the athlete's health. In this sense, among several factors that can help in this adaptation, it has been pointed out that the microbiota, which can be modulated by diet, age, medical treatments, lifestyle, and physical exercise, can favor the maintenance of a healthy status. According to the literature, both probiotics, prebiotics, and symbiotics are able to benefit people in different ways, for instance, by favoring immunoregulation, these elements can impact the prevention or decrease in the frequency and/or intensity of infections in the upper airways, both in the population in general and in athletes. However, it is noteworthy to mention that there is still a lack of reports in the scientific literature on the effects of the ingestion of fermented milk containing *Lacticaseibacillus paracasei* strain Shirota (LcS), a well-known probiotic agent, not only on the modulation of the immune/inflammatory responses, but on the manifestation of symptoms of airways and mood state in triathletes. Therefore, in this study, we aimed to investigate, in a general way, the effect of daily intake of fermented milk containing 40 billion LcS in amateur triathletes, emphasizing that our primary endpoint will be to evaluate the concentration of salivary IgA, and the secondary endpoints will be to assess both systemic immune/inflammatory and upper airway responses, as well as the incidence and duration of upper airway symptoms, and also the mood states. In order to respond to these endpoints, samples of saliva, nasal swab, and blood, as well as data regarding quality of life, upper airway symptoms manifestation, and mood states will be obtained on five different occasions: 30 days (1) and 24 hours before the competition (2), and also immediately (3), 72 hours (4), and 14 days after the competition end (5). It is important to highlight that the data related to the quality of life, upper airway symptoms manifestation, and mood states will be obtained by using specific and validated questionnaires, such as SF-36 (Short Form Health Survey 36), WURSS-21 (Wisconsin Upper Respiratory Symptom Survey – 21), and BRUMS (The Brunel Mood Scale), respectively. Finally, it is also paramount to clarify that the triathletes participating in this study will be oriented to ingest a daily bottle of fermented milk containing 40 billion LcS or placebo/unfermented milk throughout the study period, starting the ingestion

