### **Assessment of mood state**

The Brunel mood scale (BRUMS, Annex 6) will be used to assess the mood state. The BRUMS involves 24 mood indicators, divided into six subitems, namely anger, confusion, depression, fatigue, tension, and vigor. The volunteer should indicate on a scale from 0 (zero) to 4 (four) what they are feeling on the time-point of application of the BRUMS. (Rohlf, 2008).

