#### **SCHEDE OF ACTIVITIES TO BE DEVELOPED**

Parameters	Enrollment	Allocation	Intervention				
			Pre-Triathlon		Post-Triathlon		
Timepoint			-60d to -30d	-30d	-1d	0d	3d
Recruitment and selection of volunteers	X						
Informed consent	X						
Anamnesis, anthropometry, cardiopulmonary test	X						
Randomization		X					
Intervention: LcS/Placebo intake			X	X	X	X	X
Questionnaire - WURSS	X			X		X	X

Questionnaire - IPAQ	X			X			
Questionnaire - gastrointestinal problems	X			X		X	X
Questionnaire – SF36	X			X		X	X
Questionnaire – BRUMS	X			X		X	X
Questionnaire - Subjective Perception of Effort Scale	X				X		
Blood, saliva, nasal swab collection			X	X	X	X	X

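### The text promises mood, airway-symptom and quality-of-life questionnaires on all five occasions, but the schedule marks them only four times, on the best reading omitting day -30 and race day

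*Combined protocol and SAP*

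**What the plan says.** The Sample collection section defines the occasions: "Blood, saliva, and nasal swab will be collected on five different occasions: (1) before the beginning of the ingestion", then 24 hours before the race, immediately after it, 72 hours after and 14 days after. It then states that "on the same occasions, the occurrence of upper airway symptoms and mood states will also be assessed by using questionnaires". The Abstract says that samples, quality of life, airway symptoms and mood "will be obtained on five different occasions", and lists the same five times.

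The schedule of activities has one row per assessment. The row "Blood, saliva, nasal swab collection" is marked in all five intervention columns and not at enrolment. The row "Questionnaire – BRUMS" has four marks: enrolment and three of the five intervention columns. The WURSS and SF-36 rows carry the same four marks.

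The Assessment of mood state section says that volunteers report "what they are feeling on the time-point of application of the BRUMS". Mood and airway symptoms are both named in the secondary objective.

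**The concern.** Staff usually work from the schedule table. If they do so here, two of the five promised questionnaire occasions are lost and an enrolment reading takes the place of the baseline.

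Three things follow for mood:

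- **Immediate post-race reading.** The Introduction links inflammatory markers to mood and expects those markers to rise after strenuous exercise. The samples taken at the finish would have no mood score to set beside them, although the Statistical analysis section plans correlations between variables.
- **Baseline.** An enrolment reading would stand in for a reading at the first sampling visit. The hormone section uses hormone levels on the five occasions to assign menstrual phase, and the Introduction says that phase can affect mood. An enrolment mood score would have no hormone sample to go with it.
- **No repair later.** BRUMS captures the moment of completion. Multiple imputation, the plan's method for missing data, cannot rebuild an occasion on which nobody was scheduled to answer.

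**Working it through.** No statistic in the plan bears on this point. The check is a count of marks, row by row, against the occasions promised in the text.

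**Step 1: count the marks.** Promised questionnaire occasions: 5. Marks for samples: 5. Marks for BRUMS, WURSS and SF-36: 4 each, of which 1 is at enrolment, so 4 - 1 = 3 fall in intervention columns. The shortfall against the promised occasions is 5 - 3 = 2.

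**Step 2: settle which columns are empty.** In the extracted table the time-point labels are displaced against the marks and there is no 14-day label. Two alignments are possible.

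*Labels taken literally by position.* BRUMS would fall at enrolment, -30d, 0d and 3d, with nothing at -1d. This alignment does not fit the rest of the plan:

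- Product intake and sampling would begin under -60d to -30d, whereas the LcS ingestion section starts intake 30 days before the race.
- No column would remain for the 14-day sample.
- The first post-race column would be labelled -1d.

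*Labels realigned to the column headings.* There are two pre-race and three post-race columns, and samples are marked in all five. They match -30d, -1d, 0d, 3d and 14d, with -60d to -30d belonging to enrolment. The row "Questionnaire - Subjective Perception of Effort Scale" supports this, because its second mark then falls in the race-day column.

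On the realigned reading:

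| | Enrolment | -30d | -1d | 0d | 3d | 14d |
|---|---|---|---|---|---|---|
| Text: mood and symptoms (Abstract also quality of life) | | X | X | X | X | X |
| Schedule: samples | | X | X | X | X | X |
| Schedule: BRUMS, WURSS, SF-36 | X | | X | | X | X |
| Schedule: effort scale | X | | | X | | |

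The count in step 1 does not depend on this choice. Under the literal alignment, too, only three of the five promised times carry a BRUMS mark (-30d, 0d and 3d). Which two are missing does depend on it.

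**Step 3: size the consequences on the realigned reading.**

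- Post-race mood readings promised: 3 (0d, 3d, 14d). Scheduled: 2 (3d, 14d).
- Gap between enrolment mood and the -30d samples: from 30 - 30 = 0 days to 60 - 30 = 30 days. The documents do not indicate where in that range a typical volunteer would fall.

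**Step 4: compare the questionnaires.** The gap is most serious for BRUMS because it is momentary. WURSS-21 (Annex I) is a daily report covering the last 24 hours, and both the Anamnesis section and the work plan say that symptoms are followed throughout the study, although the schedule row does not show this. Many SF-36 items (Annex II) ask about the previous four weeks, so a race-day omission could be deliberate there. The gastrointestinal questionnaire has the same four marks, but neither the Abstract nor the Sample collection section promises it on the five occasions.

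**The case against.** The strongest reply is that the plan does provide for mood immediately after the race: the Abstract and the Sample collection section both say so, and nothing gives the schedule precedence. This stands. A reader might infer from the table that the acute post-race mood response is never measured. The documents do not support that, because the reading is lost only if the table is followed over the text. Figure 1, which the Sample collection section cites, was not visible in the copy reviewed and may bear on the question.

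A second reply is that the table is broken, so naming the empty cells is an inference. This also stands, in part. The realignment in step 2 is the only one found that fits the intake and sampling rules, but it is still a reading. The mismatch of four marks against five promised occasions needs no realignment.

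A reader might also rerun the sample-size calculation with four measurements instead of five and report a loss of power for mood. That is not supported. The inputs (f = 0.15, correlation 0.5) were chosen for salivary IgA. The documents give no effect size, correlation or power target for mood, and f would itself depend on which occasions are kept. The calculated 62 is also below the planned 70-80.

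Finally, two post-race mood readings remain under the schedule, and the Introduction describes inflammation as associated with mood rather than as its established cause in athletes. Both points limit how much is at stake, but they do not remove the contradiction.

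**Conclusion.** Wrong as written: an internal contradiction between the text and the schedule. The text promises five questionnaire occasions; the schedule gives four administrations, of which three fall on promised occasions. On the best reading -30d and 0d are empty. If the schedule governs, one of three post-race mood readings is lost for good, and baseline mood precedes baseline samples by anywhere from 0 to about 30 days.

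The count is firm. The identity of the empty columns, and the 0 to 30 day range, rest on the realignment of the displaced header. The same contradiction covers WURSS-21 in both text sections and SF-36 in the Abstract. The affected endpoints are secondary, and the primary salivary IgA analysis and its sample size are unaffected. It is more than a clerical slip because a missed BRUMS reading cannot be recovered, so it should be settled before the first volunteer is enrolled.

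**What to change.** Reconcile the Abstract, the Sample collection section and the schedule of activities:

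- In the schedule, mark BRUMS, WURSS-21 and SF-36 at -30d, before the first bottle, and at 0d after the race, so that they match the five occasions in the text. The enrolment administration may stay as a screening measure, provided the plan states which reading is the baseline.
- If the race-day omission is deliberate for any of these questionnaires, amend the text to say so and state which occasions its analysis will use.
- Check the time-point header in the source table, including the 14-day label, and check that Figure 1 agrees.

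The cost is a short extra form burden at two visits that athletes already attend for sampling; BRUMS has 24 items. The finish line is the less convenient of the two, but on the realigned schedule the effort scale is already completed there.
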